10. STATISTICS

10.1. Sample Size Determination

Part 1 is a single-arm open-label study. The sample size calculation is based on the primary endpoint of \geq Grade 2 CRS rate by Day 14. It was considered that $60\% \geq$ Grade 2 CRS by Day 14 is clinically relevant in this setting. Based on a target rate of 60%, a sample size of 62 will provide 90% power to exclude a higher limit of 79% of a 2-sided 95% CI. The sample size calculation is based on an efficacy evaluable analysis set (see Section [10.2](#) for definition).

[Table 18](#) represents CRS Rates and CIs for a sample size of 62.

Table 18: CRS Rates and 95% Confidence Intervals

Sample Size	Number of CRS	CRS Rate (%)	95% Confidence Interval (%)
62	36	58.1	44.8, 70.5
62	38	61.3	48.1, 73.4
62	40	64.5	51.3, 76.3
62	42	67.7	54.7, 79.1
62	44	71.0	58.1, 81.8

Part 2 is a randomized expansion of the study; itacitinib 200 mg BID versus placebo.

As in Part 1, the primary endpoint is Grade \geq 2 CRS rate by Day 14. Assuming Grade \geq 2 CRS rate in the placebo arm is 50% ([Nastoupil et al 2020](#)) and a 20% in the treatment arm (~30% change in CRS rate), a sample size of 23 evaluable participants per group would provide 70% power based on a 1-sided Type-I error rate of 5%. Sufficient number of participants will be enrolled to yield 23 evaluable participants in each group.

A Bayesian interpretation for the selection and impact of the sample size can be provided in terms posterior probabilities. As the response rate based on CRS grade has a binomial (n, p) distribution with s number of responders out of n participants, it is common to use a conjugate Beta (a, b) prior which will lead to a Beta(a + s, b + n - s) posterior distribution. For this exercise, we will assume a noninformative Beta(1,1) (~ Uniform(0,1) prior).

[Table 19](#) presents scenarios of Bayesian posterior probability of demonstrating a treatment difference ($\geq 30\%$) by Day 14 in response rates, between the itacitinib 200 mg BID group and the placebo group, under various response rates (number and percentage of responders).

Table 19: Bayesian Posterior Probability of Demonstrating a Treatment Difference

N ^a (%) 200 BID Group	N ^b (%) Placebo	Posterior Probability ^c
2 (8.7)	9 (39.1)	43.7
	12 (52.5)	79.4
	14 (60.9)	93.4
5 (21.7)	9 (39.1)	13.9
	12 (52.5)	45.9
	14 (60.9)	67.9
7 (30.4)	9 (39.1)	4.7
	12 (52.5)	22.7
	14 (60.9)	44.7

^a Number of participants with CRS \geq Grade 2, out of 23 participants, in the 200 mg BID group.

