10.5. Interim Analysis

For Part 1, an interim analysis is planned after approximately 24 participants are dosed with IEC therapy and complete the Day 28 (EOT) visit. The results from the interim analysis will be reviewed by the DSMB. The primary intent of this analysis is to minimize unnecessary exposure to itacitinib in the event of futility of preventing CRS. The study may be stopped for futility at the interim analysis if the conditional power based on interim results is lower than 20%, which is

equivalent to more than 17 out of 24 participants experiencing \geq Grade 2 CRS by Day 14. More than 24 participants may be available in EAS at the time of interim analysis, and the stopping boundary will be re-evaluated at the time of the analysis. [REDACTED]

[REDACTED] Enrollment will continue while the analysis is being conducted, and the study Statistical Analysis Plan will describe the planned interim analysis in greater detail.

No interim analysis is planned for Part 2.

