3.4. Sample Size Considerations

Part 1 is a single-arm open-label study. The sample size calculation is based on the primary endpoint of \geq Grade 2 CRS rate by Day 14. It was considered that $60\% \geq$ Grade 2 CRS by Day 14 is clinically relevant in this setting. Based on a target rate of 60%, a sample size of 62 will provide 90% power to exclude a higher limit of 79% of a 2-sided 95% CI. The sample size calculation is based on an EAS (see Section [5.3](#) for definition).

[Table 2](#) represents CRS rates and CIs for a sample size of 62.

Table 2: Cytokine Release Syndrome Rates and 95% Confidence Intervals

Sample Size	Number of CRS	CRS Rate (%)	95% CI (%)
62	36	58.1	44.8, 70.5
62	38	61.3	48.1, 73.4
62	40	64.5	51.3, 76.3
62	42	67.7	54.7, 79.1
62	44	71.0	58.1, 81.8

Part 2 is a randomized expansion of the study; itacitinib 200 mg BID versus placebo.

As in Part 1, the primary endpoint is Grade \geq 2 CRS rate by Day 14. Assuming Grade \geq 2 CRS rate in the placebo arm is 50% ([Nastoupil et al 2020](#)) and is 20% in the treatment arm (~30%

change in CRS rate), a sample size of 23 evaluable participants per group would provide 70% power based on a 1-sided Type I error rate of 5%. Sufficient number of participants will be enrolled to yield 23 evaluable participants in each group.

A Bayesian interpretation for the selection and impact of the sample size can be provided in terms posterior probabilities. As the response rate based on CRS rate has a binomial (n, p) distribution with s number of responders out of n participants, it is common to use a conjugate Beta (a, b) prior which leads to a Beta($a + s$, $b + n - s$) posterior distribution. For this exercise, we assume a noninformative Beta(1,1) (\sim Uniform(0,1) prior).

Table 3 presents scenarios of Bayesian posterior probability of demonstrating a treatment difference ($\geq 30\%$) by Day 14 in CRS rates, between the itacitinib 200 mg BID group and the placebo group, under various CRS rates assumption (number and percentage of participants experiencing \geq Grade 2 CRS).

Table 3: Bayesian Posterior Probability of Demonstrating a Treatment Difference

N^a (%) 200 BID Group	N^b (%) Placebo	Posterior Probability^c
2 (8.7)	9 (39.1)	43.7
	12 (52.5)	79.4
	14 (60.9)	93.4
5 (21.7)	9 (39.1)	13.9
	12 (52.5)	45.9
	14 (60.9)	67.9
7 (30.4)	9 (39.1)	4.7
	12 (52.5)	22.7
	14 (60.9)	44.7

^a Number of participants with CRS \geq Grade 2, out of 23 participants, in the 200 mg BID group.

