7.2. Analysis of the Primary Efficacy Parameter

7.2.1. Primary Efficacy Analysis

The primary endpoint of the study is CRS rate by Day 14, defined as the percentage of participants experiencing \geq Grade 2 CRS by Day 14 after IEC therapy.

In Part 1, the CRS rate will be calculated for each treatment group as follows:

$$\text{CRS rate} = \frac{x}{n}$$

where n is the number of efficacy evaluable participants, and x is the number of efficacy evaluable participants who experience \geq Grade 2 CRS by Day 14.

The exact 95% CI (2-sided) will be calculated using the Clopper-Pearson method ([Clopper and Pearson 1934](#)), as the following:

$$(B\left(\frac{\alpha}{2}; x, n - x + 1\right), B(1 - \frac{\alpha}{2}; x + 1, n - x))$$

where $B(p; v, w)$ is the p th percentile from a beta distribution with shape parameters v and w , and α is 5%.

In Part 2, the CRS rate and the associated 95% CI will also be calculated for each treatment group, itacitinib 200 mg BID and placebo, in the same way as the analysis for Part 1. The primary efficacy endpoint analysis will be the comparison of the percentage of efficacy evaluable participants experiencing \geq Grade 2 CRS by Day 14 between the 2 treatment groups. The CRS rates will be compared using a 1-sided Z-test at the significance level of 0.05, and a 95% CI (2-sided) for the difference in the CRS rate will be calculated. The following statistical hypothesis will be tested for the primary efficacy endpoint analysis:

$$H_0: \text{CRS}_A \geq \text{CRS}_B \text{ versus } H_1: \text{CRS}_A < \text{CRS}_B$$

where CRS_A and CRS_B will be the CRS rates for itacitinib 200 mg BID and placebo, respectively. The Z-test for the difference between the 2 treatment groups will be based on the following test statistic:

$$z = \frac{\widehat{\text{CRS}}_A - \widehat{\text{CRS}}_B}{\sqrt{\widehat{\text{CRS}}(1 - \widehat{\text{CRS}})\left(\frac{1}{n_1} + \frac{1}{n_2}\right)}}$$

where n_1 and n_2 are the numbers of efficacy evaluable participants for itacitinib 200 mg BID and placebo, respectively, and

$$\begin{aligned}\widehat{CRS}_A &= \frac{x_1}{n_1} \\ \widehat{CRS}_B &= \frac{x_2}{n_2} \\ \widehat{CRS} &= \frac{x_1 + x_2}{n_1 + n_2}\end{aligned}$$

where x_1 and x_2 are the number of efficacy evaluable participants experiencing CRS \geq Grade 2 by Day 14 for the treatment group, itacitinib 200 mg BID and placebo, respectively.

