10. INTERIM ANALYSES

For Part 1, an interim analysis is planned after approximately 24 participants are dosed with IEC therapy and complete the Day 28 (EOT) visit. The results from the interim analysis will be reviewed by the DSMB. The primary intent of this analysis is to minimize unnecessary exposure to itacitinib in the event of futility of treating CRS. The study may be stopped for futility at the interim analysis if the conditional power based on interim results is lower than 20%, which is equivalent to more than 17 out of 24 participants experiencing \geq Grade 2 CRS by Day 14. More than 24 participants may be available in EAS at the time of interim analysis, and the stopping boundary will be re-evaluated at the time of the analysis. [REDACTED]

[REDACTED] Enrollment will continue while the analysis is being conducted.

No interim analysis is planned for Part 2.

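### Part 1's stated 90% power is a single-stage figure: following the written futility rule costs about 5 to 6 points and stops a drug at the 60% target rate 9.6% of the time

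*SAP*

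**What the plan says.** Protocol 10.1 sets the size of Part 1: "Based on a target rate of 60%, a sample size of 62 will provide 90% power to exclude a higher limit of 79" percent. SAP 3.4 repeats it: "a sample size of 62 will provide 90% power to exclude a higher limit of 79% of a 2-sided 95% CI". Neither section mentions an interim look. The interval method is fixed in SAP 7.2.1: "The exact 95% CI (2-sided) will be calculated using the Clopper-Pearson method".

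SAP 10 then says that "an interim analysis is planned after approximately 24 participants are dosed with IEC therapy" and complete Day 28. The consequence is permissive: "The study may be stopped for futility at the interim analysis". The trigger, in the same section, is that "the conditional power based on interim results is lower than 20%, which is equivalent to more than 17 out of 24 participants" have Grade 2 or higher CRS by Day 14. Protocol 10.5 has the same boundary ("equivalent to more than 17 out of 24 participants experiencing" such an event), and so do the overall design sections of both documents. The boundary is not final: "More than 24 participants may be available in EAS at the time of interim analysis, and the stopping boundary will be re-evaluated".

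The visible text gives no probability of stopping at any true rate and no power that allows for the interim look. Part of the text next to the boundary is redacted in both interim sections.

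**The concern.** A futility look can only lower the chance that a trial reaches its success criterion. It removes some trials that would have recovered after a poor first stage and leaves the rest unchanged. A power statement for a design with such a look should therefore either include it or say that it does not.

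Here the loss need not be negligible. At a 60% rate, 24 × 0.60 = 14.4 events are expected in the first 24 participants, and stopping begins at 18. The data monitoring board and readers see 90% power in one section and a stopping rule in another, with nothing to show how often the rule would end the study of a drug performing exactly at the rate the plan calls clinically relevant.

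**Working it through.** **Inputs.** N = 62, target rate 0.60, limit to exclude 0.79, stated power 90% (Protocol 10.1, SAP 3.4). Clopper-Pearson two-sided 95% interval (SAP 7.2.1). Interim at 24, stop at 18 or more events (Protocol 10.5, SAP 10), leaving 62 − 24 = 38 participants for the second stage.

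**Step 1: which final count is a success.** The exact upper limit is 77.67% for 41/62 and 79.06% for 42/62; the plan's own table prints the latter as 79.1. Read strictly, excluding 79% needs 41 or fewer events. If the limit is rounded to 79%, 42 qualifies. Both cut-offs, c = 41 and c = 42, are carried forward.

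**Step 2: reproduce the 90% with no interim.** Power = P(X ≤ c), X ~ Bin(62, 0.60).

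- c = 42: 91.7%
- c = 41: 86.8%
- Arcsine approximation, two-sided 5%: 90.8%

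The stated 90% is thus matched to within 2 points by a single-stage calculation, either exact at 42 or by arcsine.

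**Step 3: probability of stopping at the interim.** P(X1 ≥ 18), X1 ~ Bin(24, p).

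- p = 0.60: 9.6%
- p = 0.79: 77.5%

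These depend only on the written boundary, not on the interval method or the final cut-off.

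**Step 4: power with the rule followed.** Sum over x = 0 to 17 of P(X1 = x) × P(X2 ≤ c − x), with X1 ~ Bin(24, 0.60) and X2 ~ Bin(38, 0.60).

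| Success if events in 62 are | Single-stage | Rule followed | Loss from rule | Share of stopped trials that would have succeeded |
|---|---|---|---|---|
| 42 or fewer | 91.7% | 85.6% | 6.1 points | 0.0610 / 0.0960 = 64% |
| 41 or fewer | 86.8% | 81.9% | 4.9 points | 0.0490 / 0.0960 = 51% |

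**Step 5: which cut-off fits the printed boundary.** The documents do not define conditional power beyond its being based on interim results. Assume the observed interim rate continues: P(X2 ≤ c − x), X2 ~ Bin(38, x/24).

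- c = 42: 30.0% at 17/24 and 7.1% at 18/24, so a 20% threshold is exactly more than 17.
- c = 41: 19.2% at 17/24 and 3.5% at 18/24, so a 20% threshold would already stop at 17. That version would stop a 60% drug 19.2% of the time and have 75.1% power.

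On this definition 42 fits both the boundary and the 90%. The definition matters: a predictive probability averaged over a uniform prior gives, at c = 41, 32.7% at 17/24 and 15.8% at 18/24, which also fits the boundary. The documents do not settle the cut-off, so both rows of the table are needed.

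**The case against.** The strongest objection is that the rule is non-binding. The study may be stopped, after board review, and need not be. It is legitimate to quote power without a non-binding futility look; that figure applies if the look is not enforced, and the losses above are the worst case. This stands, and it limits the point to labelling. It does not remove it, because neither power sentence says that the look was left out.

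Second, a reader might set 90% beside 82% and infer that the rule costs 8 points. The documents do not support that. At the strict cut-off of 41, single-stage power is already 86.8%, so about 3 of the 8 points come from the stricter final criterion and 4.9 from the rule. The 90% belongs with a cut-off of 42 (or an arcsine approximation), where the figure with the rule followed is 85.6%. Nor is 82% the only correct replacement: under conditional power at the observed rate, a cut-off of 41 does not produce the printed boundary.

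Third, the numbers hold for exactly 24 participants, while the plan says approximately 24 and allows the boundary to be re-evaluated. The reported interim had 26 participants. With a cut-off of 42 and conditional power at the observed rate, the boundary at 26 would be 19 or more (43.0% at 18, 14.6% at 19). That gives 12.2% stopping at a 60% rate and 83.8% power. So the figures move, but not back to 90%.

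Fourth, operating characteristics may lie in the redacted text, so their absence can be claimed of the visible text only. Finally, Protocol 10.3 says Part 1 has no formal hypothesis test, and Protocol 2.3.3 reports 3 of 26 participants with Grade 2 CRS and none higher, far from the boundary. Both are correct, and they confine the point to how the design is described.

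**Conclusion.** The point holds as a defect in the stated design properties. The 90% for Part 1 does not allow for the futility look. With the written rule followed at 24 participants, 90% is not reached under either exact cut-off: power is 85.6% (from 91.7%) or 81.9% (from 86.8%), a loss of 6.1 or 4.9 points due to the rule itself. The 9.6% chance of stopping a drug at the target rate follows from the boundary alone.

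The power figures assume independent participants with a common true rate of 60%, an interim at exactly 24, and the rule always obeyed. The preference for 42 rests further on an assumed definition of conditional power. It would go too far to say that the trial was underpowered in conduct or that the interim decision was affected: the rule was optional and the observed count was nowhere near it. No analysis or estimate changes.

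**What to change.** In Protocol 10.1 and SAP 3.4, say that 90% is single-stage power, applicable if the non-binding futility rule is not enforced. Add the power with the rule followed, naming the final cut-off: about 86% for success at 42 or fewer of 62, or about 82% for 41 or fewer, the strict exact-interval criterion. The sponsor should say which cut-off was intended rather than insert 82% as the sole replacement.

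In Protocol 10.5 and SAP 10, state that the boundary of more than 17 of 24 stops the study with probability 9.6% at a true rate of 60% and 77.5% at 79%. Note that these values change if the boundary is re-evaluated for more than 24 participants, and say how conditional power was defined. If the redacted text already gives these figures, a cross-reference from the power sections is enough.

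The cost is a few sentences in four sections and a less favourable stated power. No participants, procedures or analyses are added, and conduct is unchanged because the interim has passed.

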11. CHANGES AND MODIFICATIONS TO THE ANALYSIS PLAN

All versions of the SAP are listed in [Table 8](#).

Table 8: Statistical Analysis Plan Versions

SAP Version	Date
Original	06 JAN 2021
Amendment 1	08 MAY 2023

11.2. Changes to the Statistical Analysis Plan

11.2.1. Amendment 1

The primary purpose of SAP Amendment 1 is to implement Protocol Amendments 3 and 4 by adding the analyses for the randomized placebo-controlled Part 2 of the study using a 200 mg BID regimen.

Other minor updates include:

- Replaced previous IND number with a new IND number.
- Revised Section 7.2.1 to provide explanation of calculations.
- Additional analyses were added to Section 7.2.1 and Section 7.3.
- Liver function test criteria was updated to align with the new version of standard.
- Format changes were applied to Appendix A. Additional tables and listings were added.
- In Appendix A, ECG tables were deleted due to data collection, the corresponding listings will still be created.
- Editorial changes have been made for better clarity and accuracy.

APPENDIX A. PLANNED TABLES, FIGURES, AND LISTINGS

This appendix provides a list of the planned tables, figures, and listings for the Clinical Study Report. The lists of tables, figures, and listings are to be used as guidelines. Modifications of the lists that do not otherwise affect the nature of the analysis will not warrant an amendment to the SAP.

Tables

Table No.	Title	Population
Baseline and Demographic Characteristics		
1.1 Disposition		
1.1.1	Analysis Populations	Enrolled
1.1.2	Summary of Participant Disposition	Safety
1.1.3	Summary of Number of Participants Enrolled by Site	Enrolled
1.1.4	Summary of Protocol Deviations	Safety
1.2 Demography and Baseline Characteristics		
1.2.1	Summary of Demographics and Baseline Characteristics	Safety
1.3 Baseline Disease Characteristics (refine per data collection)		
1.3.1	Summary of Underlying Disease History and Baseline Disease Characteristics for B-Cell Lymphoma	Safety
1.3.2	Summary of Underlying Disease History and Baseline Disease Characteristics for Mantle Cell Lymphoma	Safety
1.3.3	Summary of Underlying Disease History and Baseline Disease Characteristics for Acute Lymphoblastic Leukemia	Safety
1.3.4	Summary of Cancer Types	Safety
1.3.5	Summary of Prior Therapy	Safety
1.4 Prior Medication and Concomitant Medication (refine per data collection)		
1.4.1	Summary of Prior Medications	Safety
1.4.2	Summary of Concomitant Medications	Safety
1.5 Others		
1.5.1	Summary of General Medical History	Safety
1.5.2	Summary of Death	
2 Efficacy (add subgroup analysis as needed)		
2.1.1	Summary of CRS Rate by Day 14 After IEC Therapy	EAS
2.1.1.1	Sensitivity Analysis: Summary of CRS Rate by Day 14 After IEC Therapy – Excluding Participants Who Drop Out of the Study Prior to Day 14 Without Experiencing \geq Grade 2 CRS	EAS
2.2.1	Summary of ICANS Rate by Day 28 After IEC Therapy	EAS
2.2.2.1	Summary of Onset and Duration of ICANS by Day 28 After IEC Therapy	EAS
2.2.2.2	Summary of Onset and Duration of ICANS During the Lifetime of the Study	EAS
2.2.3.1	Summary of Onset and Duration of CRS by Day 28 After IEC Therapy	EAS
2.2.3.2	Summary of Onset and Duration of CRS During the Lifetime of the Study	EAS
2.2.4.1	Summary of CRS-Free Survival by Day 28 After IEC Therapy	EAS
2.2.4.2	Summary of CRS Rate Within 48 Hours and by Day 28 After IEC Therapy	EAS
2.2.4.3	Summary of Tocilizumab and Corticosteroid Use for CRS Treatment	EAS
[REDACTED]	[REDACTED]	[REDACTED]
[REDACTED]	[REDACTED]	[REDACTED]

Table No.	Title	Population
[REDACTED]	[REDACTED]	[REDACTED]
[REDACTED]	[REDACTED]	E [REDACTED]
[REDACTED]	[REDACTED]	[REDACTED]
[REDACTED]	[REDACTED]	[REDACTED]
Safety		
3.1 Dose Exposure		
3.1.1	Summary of Exposure to Study Drug	Safety
3.1.2	Summary of Exposure to IEC Therapy	EAS
3.2 Adverse Events		
3.2.1.1	Overall Summary of Treatment-Emergent Adverse Events	Safety
3.2.2.1	Summary of Treatment-Emergent Adverse Events by MedDRA System Organ Class and Preferred Term	Safety
3.2.3.1	Summary of Treatment-Emergent Adverse Events by MedDRA Preferred Term in Decreasing Order of Frequency	Safety
3.2.4.1	Summary of Treatment-Emergent Adverse Events by MedDRA System Organ Class, Preferred Term, and Maximum Severity	Safety
3.2.5.1	Summary of Grade 3 or Higher Treatment-Emergent Adverse Events by MedDRA System Organ Class and Preferred Term	Safety
3.2.6.1	Summary of Grade 3 or Higher Treatment-Emergent Adverse Events by MedDRA System Organ Class, Preferred Term, and Maximum Severity	Safety
3.2.7.1	Summary of Grade 3 or Higher Treatment-Emergent Adverse Events by MedDRA Preferred Term in Decreasing Order of Frequency	Safety
3.2.8.1	Summary of Serious Treatment-Emergent Adverse Events by MedDRA System Organ Class and Preferred Term	Safety
3.2.9.1	Summary of Serious Treatment-Emergent Adverse Events by MedDRA Preferred Term in Decreasing Order of Frequency	Safety
3.2.10.1	Summary of Study Drug Treatment-Related Treatment-Emergent Adverse Events by MedDRA System Organ Class and Preferred Term	Safety
3.2.11.1	Summary of Study Drug Treatment-Related Adverse Events by MedDRA System Organ Class, Preferred Term, and Maximum Severity	Safety
3.2.12.1	Summary of IEC Therapy Treatment-Related Treatment-Emergent Adverse Events by MedDRA System Organ Class and Preferred Term	Safety
3.2.13.1	Summary of IEC Therapy Treatment-Related Adverse Events by MedDRA System Organ Class, Preferred Term, and Maximum Severity	Safety
3.2.14.1	Summary of Grade 3 or Higher Study Drug Treatment-Related Adverse Events by MedDRA System Organ Class and Preferred Term	Safety
3.2.15.1	Summary of Grade 3 or Higher IEC Therapy Treatment-Related Adverse Events by MedDRA System Organ Class and Preferred Term	Safety
3.2.16.1	Summary of Study Drug Treatment-Related Serious Treatment-Emergent Adverse Events by MedDRA System Organ Class and Preferred Term	Safety
3.2.17.1	Summary of IEC Therapy Treatment-Related Serious Treatment-Emergent Adverse Events by MedDRA System Organ Class and Preferred Term	Safety
3.2.18.1	Summary of Treatment-Emergent Adverse Events With a Fatal Outcome by MedDRA System Organ Class and Preferred Term	Safety
3.2.19.1	Summary of Treatment-Emergent Adverse Events Leading to Study Drug Dose Interruption by MedDRA System Organ Class and Preferred Term	Safety

Table No.	Title	Population
3.2.20.1	Summary of Treatment-Emergent Adverse Events Leading to IEC Therapy Interruption by MedDRA System Organ Class and Preferred Term	Safety
3.2.21.1	Summary of Treatment-Emergent Adverse Events Leading to Study Drug Dose Reduction by MedDRA System Organ Class and Preferred Term	Safety
3.2.22.1	Summary of Treatment-Emergent Adverse Events Leading to Withdrawal of Study Drug	Safety
